6.7 Early Termination Visit and Withdrawal Procedures

The end of treatment for patients completing the study is Week 28. For patients who are withdrawn from the study prior to completion, all Week 28 procedures will be performed at an Early Termination visit. The Early Termination visit may be conducted by home healthcare services (United States only). These procedures include the following:

- Record concomitant medications.
- Obtain body weight.
- Perform complete physical examination.
- Record vital signs (systolic and diastolic blood pressure, pulse rate, and body temperature).
- Perform urine or serum pregnancy test for females of childbearing potential only.
- Collect blood samples for blood biochemistry, hematology, and coagulation for analysis by the local laboratory (Japan sites) and central laboratory (US sites).
- Collect urine sample for urinalysis by the local laboratory (Japan sites) and central laboratory (US sites) (if possible).
- Collect blood sample for CMV DNA analysis by the central laboratory.
- Collect blood samples for CMV DNA analysis or CMV antigenemia testing for analysis by the local laboratory.
- Collect blood sample for serum NPC-21 concentration measurement.
- Collect blood sample for anti–NPC-21 antibody measurement.
- Collect blood samples that will be stored for screening for resistant strains analysis.
- Perform 12-lead ECG.
- Perform EQ-5D-5L.
- Record adverse events.

7 EFFICACY ASSESSMENTS

7.1 Primary Efficacy Endpoint

The primary efficacy endpoint is the incidence of CMV disease (CMV syndrome [see Appendix C for definition of CMV syndrome] or tissue-invasive CMV disease [see Appendix D for definitions of CMV disease]) or CMV viremia (defined as the detection of ≥ 250 IU/mL in plasma measured by PCR analysis in central laboratory or meets the local criteria for CMV viremia measured by PCR analysis or antigenemia testing) by Week 16.

7.2 Secondary Efficacy Endpoints

The secondary efficacy endpoints include the following:

- Incidence of CMV disease or CMV viremia by Week 28
- Incidence of CMV disease
- Incidence of CMV viremia
- Time to detectable CMV disease or CMV viremia
- Time to detectable CMV disease
- Time to detectable CMV viremia
- Amount of CMV DNA by PCR analyzed by the central laboratory
- Incidence and duration of anti-CMV therapy during the Rescue Phase
- Changes in EQ-5D-5L score from Baseline to Weeks 16 and 28

7.3 Cytomegalovirus Deoxyribonucleic Acid and Antigenemia Test

Blood samples will be collected at Screening; prior to study drug administration on dosing days (Day 1 and at Weeks 4, 8, and 12); and at Weeks 1, 2, 3, 5, 6, 7, 9, 10, 11, 13, 14, 15, 16, 17, 18, 19, 20, 21, 22, 23, 24, 26, and 28 for CMV DNA analysis utilizing PCR analysis or CMV antigenemia testing. The central laboratory will perform CMV PCR analysis, and the local laboratory will perform CMV PCR analysis or CMV antigenemia testing consistently throughout the study. Upon entering the Rescue Phase, a blood sample will be collected for CMV DNA analysis utilizing PCR analysis performed by the central laboratory. Samples for evaluation by the central laboratory may be collected by home healthcare services (United States only) at non-dosing day visits.

Home healthcare services (United States only) may be utilized for CMV PCR analysis at the central laboratory. In the case home healthcare services (United States only) are utilized, it is not necessary to collect blood samples for CMV DNA analysis or CMV antigenemia testing for analysis by the local laboratory. See the study reference manual for details.

7.4 EuroQol 5 Dimensions 5 Levels Questionnaire

The EQ-5D-5L (paper version) will be performed prior to study drug administration on Day 1, at Weeks 16 and 28, and at the initiation of the Rescue Phase. The EQ-5D-5L may be performed by home healthcare services (United States only) at non-dosing day visits.

8 IMMUNOGENICITY AND VIROLOGY ASSESSMENTS

8.1 Anti-NPC-21 Antibody

The immunogenicity of NPC-21 in CMV seronegative patients will be evaluated by anti-NPC-21 antibody testing. Blood will be drawn prior to study drug administration on dosing days (Day 1 and at Weeks 4, 8, and 12) and at Weeks 16 and 28 for anti-NPC-21 antibody measurements. Samples may be collected by home healthcare services (United States only) at non-dosing day visits.

8.2 Screening for Resistant Strains Analysis

Antiviral resistance in CMV seronegative patients will be evaluated by resistant strains genotypic analysis. Blood samples will be stored for screening for resistant strains analysis and will be collected prior to study drug administration on Day 1, at Weeks 16 and 28, and at the initiation of the Rescue Phase. Samples may be collected by home healthcare services (United States only) at non-dosing day visits. The resistant strains analysis of blood samples from patients with treatment failure will be conducted in this Phase 2 study based on analysis study protocol.

9 SAFETY ASSESSMENTS

9.1 Adverse Events

An adverse event is defined as any untoward medical occurrence in a clinical investigation patient administered a pharmaceutical product, which does not necessarily have a causal relationship with this treatment. An adverse event can therefore be any unfavorable and/or unintended sign (including an abnormal laboratory finding), symptom, or disease temporally associated with the use of an investigational medicinal product, whether or not related to the investigational medicinal product. All adverse events, including observed or volunteered problems, complaints, or symptoms, are to be recorded on the appropriate eCRF.

Adverse events, which include clinical laboratory test variables, will be monitored and documented from the time informed consent is obtained until Week 28. Should the patient terminate the study early, SAEs should be reported up until the Early Termination visit or 90 days after the last administration of study drug, whichever is later. Patients should be instructed to report any adverse event that they experience to the Investigator, whether or not they think the event is due to study drug. Beginning at the time informed consent is obtained, Investigators should make an assessment for adverse events at each visit and record the event on the appropriate adverse event eCRF.

Wherever possible, a specific disease or syndrome rather than individual associated signs and symptoms should be identified by the Investigator and recorded on the eCRF. However, if an observed or reported sign or symptom is not considered a component of a specific disease or syndrome by the Investigator, it should be recorded as a separate adverse event on the eCRF. Additionally, the condition that led to a medical or surgical procedure (eg, surgery, endoscopy, tooth extraction, or transfusion) should be recorded as an adverse event, not the procedure itself.

Any medical condition already present at the time of signing informed consent should be recorded as medical history and not be reported as an adverse event unless the medical condition or signs or symptoms present at Baseline changes in severity, frequency, or seriousness at any time during the study. In this case, it should be reported as an adverse event.

Laboratory Abnormalities

Clinically significant abnormal laboratory or other examination (eg, ECG, CMV testing) findings that are detected during the study or are present at the time informed consent is obtained and significantly worsen during the study should be reported as adverse events, as described below. The Investigator will exercise his or her medical and scientific judgment in deciding whether an abnormal laboratory finding or other abnormal assessment is clinically significant. Clinically significant abnormal laboratory values occurring during the clinical study will be followed until repeat tests return to normal, stabilize, or are no longer clinically significant. Abnormal test results that are determined to be an error should not be reported as an adverse event. Laboratory abnormalities or other abnormal clinical findings (eg, ECG abnormalities) should be reported as an adverse event if any of the following are applicable:

- If an intervention is required as a result of the abnormality
- If action taken with study drug is required as a result of the abnormality
- Based on the clinical judgment of the Investigator

Where possible, the specific disease or syndrome that caused the abnormal laboratory result should be recorded as the adverse event term.

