4.3 Withdrawal Criteria

Patients may be discontinued from study drug for any of the following reasons:

- The patient no longer meets all inclusion criteria or meets any exclusion criteria and is found to be ineligible for participation through procedures (eg, medical examinations) performed after Randomization.
- Occurrence of any medical condition or circumstance that exposes the patient to substantial risk and/or does not allow the patient to adhere to the requirements of the protocol.

- Any SAE, clinically significant adverse event, severe laboratory abnormality, intercurrent illness, or other medical condition that indicates to the Investigator that continued participation is not in the best interest of the patient.
- Pregnancy.
- Requirement of the following therapy:
 - CMV hyperimmune globulin (eg, CytoGam®).
 - IVIg.
 - Plasmapheresis.
- Patient failure to comply with protocol requirements or study-related procedures and the Investigator considers it inappropriate to administer the study drug.
- Initiation of Rescue Phase.

Patients who discontinue study drug for any reason should be followed per the study schedule of events until the end of study participation.

Participation of a patient in this clinical study may be discontinued for any of the following reasons:

- The patient withdraws consent or requests discontinuation from the study for any reason.
- Termination of the study by the Sponsor or the regulatory authority.
- If a patient develops COVID-19 and is unable to continue with study visits and observations, the patient should be discontinued from the study and standard of care CMV treatment should be initiated, if necessary. If COVID-19 treatment will be provided to the patient, the Investigator should notify the Medical Monitor prior to study discontinuation, if possible. All patients should be followed for safety and resolution of COVID-19 infection. Patients who are able to complete study-related visits as an outpatient or via home healthcare services (United States only) or are inpatient and can receive study treatment will be allowed to continue to participate in the study if they do not receive any experimental treatments for COVID-19.

In the case of patients lost to follow-up, attempts to contact the patient must be made and documented in the patient's medical records.

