6.6 Rescue Phase

After first study drug administration, patients who develop detectable CMV disease (CMV syndrome [see Appendix C for definition of CMV syndrome] or tissue-invasive CMV disease [see Appendix D for definitions of CMV disease]) or CMV viremia (defined as the detection of ≥ 250 IU/mL in plasma measured by PCR analysis in central laboratory or meets the local criteria for CMV viremia measured by PCR analysis or antigenemia testing) can enter the Rescue Phase of the study and be treated by anti-CMV agents per local standard of care until the patient is negative for CMV viremia, has recovered from CMV disease, or up to Week 28, whichever comes first. When this rescue therapy is completed, the Rescue Phase is terminated at least 4 Study Weeks after the last study drug administration and all Week 28 procedures will be performed as per Section 6.7 Early Termination Visit and Withdrawal Procedures.

Note: Collection of blood samples for serum NPC-21 concentration measurement at Weeks 4, 8, and 12 during the Rescue Phase will be handled in the same manner as visits without study drug administration.

Note: If the patient is negative for CMV viremia or has recovered from CMV disease before 4 Study Weeks have passed following last study drug administration, weekly scheduled visits are not required. The Rescue Phase visits may be conducted by home healthcare services (United States only). The Rescue Phase procedures may be performed at the next scheduled visit after detecting CMV viremia or CMV disease with or without anti-CMV agents per local standard of care. Some Investigators may prescribe anti-CMV agents (eg, VGCV) in advance and instruct the patient to start taking the drug as soon as possible for safety if the disease or viremia develops. If this is the case, the Rescue Phase procedures may be performed at the next scheduled visit.

The following procedures will be performed upon entering the Rescue Phase:

- Record the rescue in IRT.
- Record concomitant medications.
- Record the date and reason for entering the Rescue Phase.
- Perform complete physical examination.
- Collect blood sample for CMV DNA analysis by the central laboratory.
- Collect blood samples that will be stored for screening for resistant strains analysis.
- Perform EQ-5D-5L.
- Record adverse events.

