3.7.1 Adverse Events

AEs will be monitored and documented from the time informed consent is obtained until Week 28. All AEs will be coded using MedDRA v24.0.

Treatment-emergent AEs (TEAEs) are defined as AEs that start on or after the first dose of study drug.

Events of serious hypersensitivity that are Grade 3 or higher or lead to treatment study drug discontinuation and vacuolization associated with immunoglobulin will be monitored as AESIs.

An overview of AEs will be provided including counts and percentages of patients (and event counts) with the following:

- Any TEAEs
- Any Grade 3 or higher TEAEs
- Any study drug related TEAEs
- Any study drug related Grade 3 or higher TEAEs
- Any AEs related to anti-CMV rescue medication
- Any AESIs
- Any Grade 3 or higher AESIs
- Any SAEs
- Any treatment-emergent serious AEs (TESAEs)
- Any TEAEs leading to discontinuation of study drug
- Any TEAEs leading to discontinuation of study
- Any AEs leading to death
- Any AEs related to COVID-19

Numbers and percentages of patients will also be presented by SOC and PT for each category in the summary tables.

Listings will be presented for AEs, Grade 3 or higher AEs, SAEs and TEAEs leading to discontinuation of study drug.

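### CMV endpoint events can enter the adverse event overview rows, and the SAP plans no CMV-excluded counterpart; the effect could be large only for study drug discontinuation, where the coding is not settled

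*Protocol*

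**What the plan says.** **Reporting.** Protocol 9.1 defines an adverse event to include "any unfavorable and/or unintended sign (including an abnormal laboratory finding), symptom, or disease temporally associated with the use of an investigational medicinal product", which covers CMV disease. Its paragraph on laboratory abnormalities names CMV testing: "Clinically significant abnormal laboratory or other examination (eg, ECG, CMV testing) findings that are detected during the study" should be reported. Two of the listed triggers are "If an intervention is required as a result of the abnormality" and "If action taken with study drug is required as a result of the abnormality". Judgment is kept: "The Investigator will exercise his or her medical and scientific judgment in deciding whether an abnormal laboratory finding" is clinically significant. Neither document exempts efficacy endpoint events.

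**Rescue.** Under Protocol 6.6, patients with CMV disease or viremia "can enter the Rescue Phase of the study and be treated by anti-CMV agents per local standard of care". The same section allows rescue procedures with or without antivirals, and lists adverse event recording and the date and reason for rescue among the entry procedures. The footnote to the study schematic in Protocol 3.1 reads as if the move to rescue were automatic. Protocol 4.3 lists "Initiation of Rescue Phase" as a reason for stopping study drug, in a bullet separate from the one on serious or clinically significant adverse events.

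**Analysis.** SAP 3.7.1 counts every adverse event from first dose as treatment-emergent. It plans overview rows for any TEAE, Grade 3 or higher, SAEs and TESAEs, and "Any TEAEs leading to discontinuation of study drug", among others, each also broken down by SOC and PT. No row leaves out CMV events.

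**The concern.** Safety is half of the primary objective. The trial is designed on the expectation that CMV events occur twice as often on placebo as on 6 mg/kg. A safety row that takes in a large share of those events will favour NPC-21 even if the drug has no safety advantage, and it could offset a real excess of other events on NPC-21.

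The SOC and PT tables show CMV terms on their own lines. They do not give the number of patients with at least one non-CMV event, because a patient may appear under several terms. The row for events related to rescue medication isolates drug toxicity, not the CMV event. The disposition table in SAP 3.3.1 counts rescue entries and reasons for stopping, but not patients who stopped because of a non-CMV adverse event.

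**Working it through.** **Inputs from the documents** (Protocol 10.2.7): CMV endpoint rate by Week 16 of 60% on placebo and 30% on 6 mg/kg; 48 per arm; two-sided 0.05; 80% power; 15% early discontinuation.

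**The plan's own figure.** Unpooled two-proportion formula: (1.96 + 0.8416)² × (0.6 × 0.4 + 0.3 × 0.7) / 0.3² = 39.2, so 40 per arm; 40 / 0.85 = 47.1, so 48. The stated 48 reproduces.

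**Assumptions not in the documents**, shown as ranges: b, the proportion of patients with a non-CMV event in a given row; f, the share of CMV endpoint events that are coded into that row; and independence of CMV and non-CMV events.

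**Formula.** Row rate = 1 − (1 − b)(1 − f × p), with p = 0.60 on placebo and 0.30 on NPC-21.

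**Discontinuation row, no true safety difference (b = 5% in both arms).** For example, at f = 0.5 placebo is 1 − 0.95 × 0.70 = 33.5% and NPC-21 is 1 − 0.95 × 0.85 = 19.3%. The last column is the NPC-21 non-CMV rate at which the two arms would look equal, 1 − 0.95(1 − 0.6f)/(1 − 0.3f).

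| f | Placebo | NPC-21 6 mg/kg | NPC-21 non-CMV rate for equality |
|---|---|---|---|
| 0 | 5.0% | 5.0% | 5.0% |
| 0.1 | 10.7% | 7.9% | 7.9% |
| 0.25 | 19.3% | 12.1% | 12.7% |
| 0.5 | 33.5% | 19.3% | 21.8% |
| 1 | 62.0% | 33.5% | 45.7% |

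**What f is made of.** For this row, f is the share of CMV events that occur while doses remain, times the share of the resulting stops that are coded as due to a TEAE. Dosing ends at Week 12 and the planned rates run to Week 16, so f = 1 is a ceiling. If 75% occur in time and one third are so coded, f = 0.25. If rescue stops are coded only under their own reason, f = 0.

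**A true excess.** Take non-CMV discontinuation of 5% on placebo and 20% on NPC-21, a difference of 15 points.

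| f | Placebo | NPC-21 | Difference (points) | Chance that the row shows more NPC-21 than placebo patients, 48 per arm |
|---|---|---|---|---|
| 0 | 5.0% | 20.0% | +15.0 | 99% |
| 0.1 | 10.7% | 22.4% | +11.7 | 92% |
| 0.25 | 19.3% | 26.0% | +6.7 | 75% |
| 0.5 | 33.5% | 32.0% | −1.5 | 40% |
| 1 | 62.0% | 44.0% | −18.0 | 3% |

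The excess cancels where 0.95(1 − 0.6f) = 0.80(1 − 0.3f), that is f = 0.15/0.33 = 0.45.

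**Other rows.** An SAE needs one of the outcomes in Protocol 9.2, so viremia alone does not qualify. At an assumed f = 0.1 and b = 5%, the SAE row is 10.70% against 7.85%, a gap of 2.85 points with no true difference. For any TEAE with an assumed background of 90%, even f = 1 gives 1 − 0.1 × 0.4 = 96% against 1 − 0.1 × 0.7 = 93%, a gap of 3.0 points. The Grade 3+ row was not quantified.

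**The case against.** The strongest reply is that the distortion rests on a coding rule that the documents do not contain. Reporting of viremia is subject to judgment, rescue entry is worded as permitted, antivirals are optional, and rescue is a stopping reason of its own. Nothing says that a rescue stop is recorded as a discontinuation due to a TEAE. This stands. It is why the result must be shown from f = 0 upward, and it is a reason to settle the coding.

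Much is also visible already. Every category is shown by SOC and PT. Events, serious events and discontinuation events are listed. Drug-related events have their own rows, and CMV infection should seldom enter them, because Protocol 9.1.3 defines a related event as one with no other identifiable cause. The DSMB sees unblinded individual data. Safety is descriptive, with no test or decision rule on these rows. With about 108 patients, someone holding the listings could count non-CMV discontinuations by hand. This lowers the stakes, but it leaves the summary tables without the count.

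A CMV-free row is not a clean contrast either. It still contains rescue-drug toxicity, expected more often on placebo. Moreover, patients who have stopped for rescue cannot later stop for another TEAE. This removes more placebo than NPC-21 patients from risk, and the independence formula ignores it. Both points stand, so there is no case for making the CMV-free version the main comparison.

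A reader might go further and infer that every endpoint event must be reported, so that the TEAE, SAE and discontinuation rows all repeat the efficacy result. The documents do not support that: reporting of viremia is a matter of judgment, SAEs need a seriousness outcome, and a row near its ceiling can move little.

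**Conclusion.** The point holds in a limited form. CMV disease, and viremia that leads to treatment or action on study drug, are reportable as adverse events. No exemption exists, and the SAP plans no overview row for patients with at least one non-CMV event.

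Only the discontinuation row could be seriously affected, and its size is unknown because f is unknown. With equal safety, the apparent advantage for NPC-21 runs from nil at f = 0, through 7.1 points at f = 0.25 and 14.3 at f = 0.5, to a ceiling of 28.5 at f = 1. The SAE and any-TEAE rows probably shift by about 3 points. These figures rest on the planned 60% and 30%, on assumed background rates and shares, and on independence.

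This is a cheap improvement to how the safety half of the objective is read. It is not evidence that a safety signal would go unseen.

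**What to change.** In SAP 3.7.1:

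- Keep all the all-event rows. Beside them add rows for TEAEs, Grade 3 or higher TEAEs, SAEs and TESAEs, and TEAEs that led to stopping study drug, each excluding a fixed list of terms for CMV viremia, CMV syndrome and tissue-invasive CMV disease.
- State whether a rescue-driven stop counts as a TEAE leading to discontinuation of study drug, so that sites and programmers treat it alike.
- State beside the table that the CMV-excluded rows still contain rescue-drug toxicity, and that patients already stopped for rescue can no longer stop for another reason.

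The permissive rescue wording in Protocol 6.6 and the automatic wording of the schematic footnote should also be reconciled, since f depends partly on which was followed.

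The cost is a term list, a few lines of SAP text and one repeated overview table. No new data are needed, and collection and reporting do not change. The SAP Addendum, Section 1, records database lock on 30 March 2023, so an addition after that date must be dated and labelled as post-lock.

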9.1.1 Adverse (Drug) Reaction

All noxious and unintended responses to a medicinal product related to any dose should be considered an ADR. “Responses” to a medicinal product means that a causal relationship between a medicinal product and an adverse event is at least a reasonable possibility, ie, the relationship cannot be ruled out.

9.1.2 Unexpected Adverse Drug Reaction

An Unexpected Adverse Drug Reaction is defined as an adverse reaction, the nature or severity of which is not consistent with the applicable product information. For NPC-21 the reference safety information is included in the Investigator’s Brochure currently in force. The reference safety information will be reviewed yearly and the periodicity of the review will be harmonized with the reporting period of the Development Safety Update Report. Any adverse event that is both unexpected (not consistent with the applicable product information) and also meets the definition of an SAE/serious adverse reaction (SAR) would be considered a Suspected Unexpected Serious Adverse Reaction (SUSAR).

